7.7.1 Criteria for Re-Starting Tenalisib after Drug toxicity

Treatment continuation in the study is at the discretion of the treating Investigator. In the absence of unacceptable toxicities or disease progression, patients may continue treatment with Tenalisib as long as:

- Absolute neutrophil count has returned to baseline, or $>750/\mu\text{L}$. Platelet count is $>50,000/\mu\text{L}$.
- Recovered from grade 3-4 non-hematologic toxicity to grade 2 or baseline (excluding alopecia). Treatment may be delayed for up to 2 weeks to recover from toxicity.
- No clinical or radiographic evidence of disease progression.
- If treatment is delayed > 2 weeks due to toxicity, because of an adverse event, treatment initiation should be discussed and agreed with the Medical Monitor.

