7.6.1 Hematological DLTs

- Grade 4 neutropenia that does not resolve to \leq Grade 3 within 14 days with supportive treatment (e.g. growth factors) **OR** Grade ≥ 3 Febrile neutropenia (ANC $<1000/\mu\text{L}$ with fever $>38.5^\circ\text{C}$ [101°F] that does not resolve to \leq Grade 2 within 14 days with supportive treatment.

- Grade 4 thrombocytopenia that does not resolve to \leq Grade 3 within 14 days with supportive treatment **OR** Grade ≥ 3 thrombocytopenia associated with Grade >2 bleeding that does not resolve to \leq Grade 2 within 14 days with supportive treatment.

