7.7 Dose Modifications

All dose modifications are graded by the CTCAE v5.0.

Note: If cytopenia events are deemed related to the underlying disease rather than either Tenalisib or Romidepsin, dose reduction will be done as per the investigator's discretion.

Patients who experience either a DLT or an adverse event meeting DLT criteria (that occurs after the DLT assessment window) will be allowed to delay dosing in order to recover from the toxicity. Patients may resume Tenalisib, provided that the toxicity has resolved to Grade ≤ 2 or baseline. If study drug is delayed >2 weeks due to drug toxicity, treatment initiation should be discussed and agreed with the Medical Monitor.

Dose reductions will be permanent. A dose re-escalation are not permitted for patients who previously had a dose reduction. Holidays from study drug are discouraged. Any patient in whom similar toxicity recurs at the reduced dose should be discontinued from further Tenalisib treatment. Note: In exceptional case, a patient may be allowed following a careful assessment of benefit and risk by the investigator and with approval from the Medical Monitor.

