7.7.2.1 Tenalisib Dose Modifications for Hematologic Toxicity

The dose modification guidelines are intended to be applied when the investigator determines the events related to Tenalisib.

Table 7: Dose Modifications for Hematologic Toxicity

Worst CTCAE Grade Toxicity	Action to be Taken
HEMATOLOGIC	
Neutropenia (ANC)	
Grade 3 $1.0 \times 10^9 / L < ANC \geq 0.5 \times 10^9 / L$	Maintain dose level. Monitor ANC at least weekly. Restart Tenalisib when the event resolved to \leq Grade 2 or baseline.
Grade 4 $0.5 \times 10^9 / L < ANC$	First incidence: Hold* dose until resolved to \leq Grade 2 or baseline, Restart Tenalisib at one dose lower . Subsequent occurrence: Hold dose until resolved to \leq Grade 2 or baseline, consider growth factor support. Discontinue if further dose modification required.
Grade 3 Febrile neutropenia ANC $< 1000 / \text{mm}^3$ with a single temperature of $> 38.3^{\circ}\text{C}$ (101°F) or a sustained temperature of $\geq 38^{\circ}\text{C}$ (100.4°F) for more than one hour.	Hold* dose until resolved to \leq Grade 2 or baseline, consider growth factor support, then restart Tenalisib at one dose lower .
Thrombocytopenia	
Grade 3 ($50.0 \times 10^9 / L < PLT \geq 25.0 \times 10^9 / L$)	Maintain dose level. Monitor ANC at least weekly. Restart Tenalisib when the event resolved to \leq Grade 2 or baseline.
Grade 4 $25.0 \times 10^9 / L < PLT$ Or thrombocytopenia that requires platelet transfusion	1st occurrence: Hold** dose until to \leq Grade 2 or baseline, Restart Tenalisib at one dose lower. Subsequent Occurrences: Hold dose until to \leq Grade 2 or baseline, consider platelet transfusion as necessary. Discontinue if further dose modification required.

*If study drug is delayed > 2 weeks because of an adverse event, treatment strategy should be discussed with medical monitor.

** Patient receiving concomitant medication (e.g. anticoagulants, anti-platelets, aspirin, or low molecular weight heparin) must be discussed with the medical monitor for continued management.

Table 8: Dose Modifications for Non-Hematologic Toxicities

NON-HEMATOLOGIC	Action to be Taken
Renal*	If serum creatinine is Grade 3 ($> 3 \times$ baseline or $> 3 \times$ ULN), hold dose until \leq grade 2. Monitor serum creatinine at least twice a week until resolution to \leq grade 2, and then at least one week until it resolves to \leq grade 1.

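### After a Tenalisib hold for Grade 4 neutropenia attributed to Tenalisib alone, Protocol 7.7.1 allows restart at ANC >750/µL while Table 7 requires Grade ≤2 (≥1,000/µL) or baseline, and no precedence is stated

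*Protocol*

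**What the plan says.** Three parts of the Protocol bear on restarting Tenalisib after neutropenia.

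- **Section 7.7.1** carries a heading about restarting Tenalisib after drug toxicity. It leaves continuation to the investigator and says that "patients may continue treatment with Tenalisib as long as" certain conditions are met. The neutrophil condition is "Absolute neutrophil count has returned to baseline, or" is above 750/µL.
- **Table 7 (Section 7.7.2.1)** applies to events that the investigator relates to Tenalisib. For Grade 4 neutropenia it reads "First incidence: Hold* dose until resolved to" Grade ≤2 or baseline, with restart one dose lower. A later occurrence is held to the same recovery level. The Grade 3 row opens with "Maintain dose level. Monitor ANC at least weekly", yet the same cell also says "Restart Tenalisib when the event resolved to" Grade ≤2 or baseline. The febrile neutropenia row holds to Grade ≤2 or baseline, then says "consider growth factor support, then restart Tenalisib at one dose lower".
- **The introduction to Section 7.7** says "Patients may resume Tenalisib, provided that the toxicity has resolved to Grade" ≤2 or baseline, but only for DLTs and for later events that meet DLT criteria.

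Section 7.7.2 has one tie-break: an event possibly related to both drugs takes the stricter modification. The SAP does not address restart rules.

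**The concern.** Both provisions apply to a patient coming off a Tenalisib hold for Grade 4 neutropenia, and they name different neutrophil counts. A site working from 7.7.1 could re-dose such a patient at, say, 800/µL, still in the Grade 3 range. A site working from Table 7 would keep the patient on hold. Both could claim to follow the protocol.

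The event is foreseen: Section 3.4.5.1 names neutropenia among the events reported with Tenalisib. What is at stake is the safety margin at re-dosing and consistent handling across about 15 centers.

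**Working it through.** **Step 1. Put the limits in one unit.** Table 7's Grade 3 band has edges 0.5 and 1.0 × 10⁹/L, that is, 500 and 1,000/µL. The inequality signs are printed the wrong way round, but the edges are clear. Hence Grade ≤2 means ANC ≥1,000/µL and Grade 4 means ANC <500/µL. The 1,000/µL figure is not printed as a restart limit; it follows from the band.

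**Step 2. Compare the rules after a Grade 4 hold.**

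| ANC (/µL) | 7.7.1 | Table 7, Grade 4 row |
|---|---|---|
| 750 or less | no restart, unless baseline | hold, unless baseline |
| above 750, below 1,000 | restart allowed | hold, unless baseline |
| 1,000 or more | restart allowed | restart allowed |

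The margin above the Grade 4 limit at restart is just over 750 − 500 = 250/µL under 7.7.1, against at least 1,000 − 500 = 500/µL under Table 7.

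**Step 3. Check whether other text closes the gap.**

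- *The baseline alternative.* Section 4.1 requires ANC ≥1,000/µL at entry. A baseline inside the band would need a fall between screening and C1D1.
- *The 7.7 introduction.* Under 7.6.1 the DLT is "Grade 4 neutropenia that does not resolve to" Grade ≤3 within 14 days. A shorter Grade 4 episode without fever falls outside the introduction's resume rule, so only 7.7.1 and Table 7 apply to it.
- *The tie-break in 7.7.2.* It covers events possibly related to both drugs, not events attributed to Tenalisib alone.
- *The Grade 3 row.* Table 7 is indexed by worst grade, so a Grade 4 event recovering through the Grade 3 range stays on the Grade 4 row.

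**Step 4. Check the companion limit.** The platelet condition in 7.7.1 is >50,000/µL, and Table 7's Grade 2/3 platelet edge is 50 × 10⁹/L = 50,000/µL. These agree. The neutrophil figure is the one that falls inside the Grade 3 band.

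**Step 5. Bound the number of patients.** Section 1.1.2 lists 1 treatment-related Grade ≥3 neutropenia among 58 patients on single-agent Tenalisib.

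- Rate: 1/58 = 0.0172, or 1.7%.
- Exact (Clopper-Pearson) 95% limits: lower 1 − 0.975^(1/58) = 0.00044; upper, the p solving (1−p)^58 + 58p(1−p)^57 = 0.025, is 0.0924.
- Planned maximum: 18 + 24 = 42 patients.
- Expected with Grade ≥3: 42 × 0.0172 = 0.72; limits 42 × 0.00044 = 0.02 and 42 × 0.0924 = 3.88.

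This counts any Grade ≥3 event. The affected group is smaller: Grade 4 only, attributed to Tenalisib alone, and with a count taken while ANC lies in the band.

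**The case against.** The strongest reply is that the texts can be read together. The 7.7.1 wording is permissive, it starts from investigator discretion and the absence of unacceptable toxicity, and its list reads naturally as minimum conditions. Table 7 is specific and directive. A site that follows Table 7 never breaches 7.7.1. This is a sensible reading, and the fix adopts it. But the protocol does not state it, and the heading of 7.7.1 presents its list as the restart criteria. An ambiguity about a safety threshold remains.

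The second reply is that little safety is lost. The Grade 3 row leads with keeping the dose across 500 to 999/µL, so on that instruction the protocol accepts dosing at these counts. Nor does 7.7.1 remove the dose reduction after a first Grade 4 event. This stands, and it keeps the point minor.

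The third reply is that the patient estimate overstates the affected group. This also stands. The single event in the earlier study may have been Grade 3. Romidepsin itself causes neutropenia (Section 3.4.5.2), and toxicity is presumed related unless clearly explained otherwise, so many events will be attributed to both drugs and take the stricter rule.

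A reader might extend the point to uncomplicated Grade 3 or to febrile neutropenia. The documents do not support that firmly. The Grade 3 cell contains both a maintain and a restart instruction and is unclear in itself. The febrile row prints no neutrophil count for recovery.

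**Conclusion.** The inconsistency is real and minor. For Grade 4 neutropenia attributed to Tenalisib alone, 7.7.1 permits restart and Table 7 forbids it when ANC is above 750 and below 1,000/µL, and no text ranks the two.

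The figure of 0.7 patients (0.02 to 3.9 of 42) is a ceiling, not a forecast. It assumes that the n=1 in the earlier study counts patients and that the single-agent rate carries over to Tenalisib-attributed events in the combination. The documents give no Grade 4 count, and the number actually affected may be zero.

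A reader might infer that DLT counts or the MTD are at risk. The documents do not show this. The criterion for Grade 4 neutropenia without fever turns on recovery to Grade ≤3, that is, ANC ≥500/µL, within 14 days, and both restart limits lie above that. No endpoint, sample size or SAP analysis uses the restart threshold.

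**What to change.** Add to Section 7.7.1:

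> After a Tenalisib hold for Grade 4 neutropenia, the >750/µL figure does not apply. Where restart is otherwise allowed under Section 7.7 (including the rule to discontinue if similar toxicity recurs at the reduced dose), Tenalisib restarts only when ANC is ≥1,000/µL (Grade ≤2) or baseline, at one dose lower after a first event, as in Table 7.

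The clause on recurrence matters. A bare statement that Table 7 governs could be taken to override the stricter instruction in the 7.7 introduction to stop Tenalisib when similar toxicity returns at the reduced dose.

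Three things should stay as they are. Set no new neutrophil figure for febrile neutropenia, because its Table 7 row prints none. Do not raise the general continuation figure in 7.7.1, because that would widen its clash with keeping the dose in the Grade 3 band. Leave the Grade 3 row unchanged in this edit.

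The cost is a short protocol clarification and a somewhat longer hold for the few patients recovering between 750 and 1,000/µL. Delays beyond 2 weeks already go to the Medical Monitor under 7.7 and 7.7.1.

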7.7.2 Dose modifications

The dose modification guidelines are intended to be applied when the investigator determines the events to be related to either one of the investigational product.

- *In case the investigator determines the events to be related to Romidepsin, Tenalisib can be continued depending on toxicity at discretion of investigator.*
- *Similarly, in case the investigator determines the events to be related to Tenalisib, Romidepsin can be continued depending on toxicity at discretion of investigator.*
- *In case the event is possibly related to Romidepsin as well as Tenalisib, the most conservative approach of dose modification should be used.*

7.7.2.1 Tenalisib Dose Modifications for Hematologic Toxicity

The dose modification guidelines are intended to be applied when the investigator determines the events related to Tenalisib.

Table 7: Dose Modifications for Hematologic Toxicity

Worst CTCAE Grade Toxicity	Action to be Taken
HEMATOLOGIC	
Neutropenia (ANC)	
Grade 3 $1.0 \times 10^9 / L < ANC \geq 0.5 \times 10^9 / L$	Maintain dose level. Monitor ANC at least weekly. Restart Tenalisib when the event resolved to \leq Grade 2 or baseline.
Grade 4 $0.5 \times 10^9 / L < ANC$	First incidence: Hold* dose until resolved to \leq Grade 2 or baseline, Restart Tenalisib at one dose lower . Subsequent occurrence: Hold dose until resolved to \leq Grade 2 or baseline, consider growth factor support. Discontinue if further dose modification required.
Grade 3 Febrile neutropenia ANC $< 1000 / \text{mm}^3$ with a single temperature of $> 38.3^{\circ}\text{C}$ (101°F) or a sustained temperature of $\geq 38^{\circ}\text{C}$ (100.4°F) for more than one hour.	Hold* dose until resolved to \leq Grade 2 or baseline, consider growth factor support, then restart Tenalisib at one dose lower .
Thrombocytopenia	
Grade 3 ($50.0 \times 10^9 / L < PLT \geq 25.0 \times 10^9 / L$)	Maintain dose level. Monitor ANC at least weekly. Restart Tenalisib when the event resolved to \leq Grade 2 or baseline.
Grade 4 $25.0 \times 10^9 / L < PLT$ Or thrombocytopenia that requires platelet transfusion	1st occurrence: Hold** dose until to \leq Grade 2 or baseline, Restart Tenalisib at one dose lower. Subsequent Occurrences: Hold dose until to \leq Grade 2 or baseline, consider platelet transfusion as necessary. Discontinue if further dose modification required.

*If study drug is delayed > 2 weeks because of an adverse event, treatment strategy should be discussed with medical monitor.

** Patient receiving concomitant medication (e.g. anticoagulants, anti-platelets, aspirin, or low molecular weight heparin) must be discussed with the medical monitor for continued management.

Table 8: Dose Modifications for Non-Hematologic Toxicities

NON-HEMATOLOGIC	Action to be Taken
Renal*	If serum creatinine is Grade 3 ($> 3 \times$ baseline or $> 3 \times$ ULN), hold dose until \leq grade 2. Monitor serum creatinine at least twice a week until resolution to \leq grade 2, and then at least one week until it resolves to \leq grade 1.
Hepatic*	Transaminitis Grade ≥ 1 Transaminitis ($ALT/AST > 1-3 \times$ ULN): • Maintain Tenalisib dose and initiate prednisone 40 mg daily .

	
 Monitor AST/ALT weekly until resolved and then taper steroid. Withhold Tenalisib in case of development of grade 2 transaminitis or worsening of Grade 1 transaminitis while on steroids. 
Grade \geq 3 Transaminitis (ALT/AST $>5-20$ X ULN):
 
 Withhold Tenalisib and monitor ALT/AST twice a weekly until Grade \leq 1; restart Tenalisib at one dose lower. Initiate prednisone 1 mg/kg in case no improvement with discontinuation of Tenalisib in 1 week. Monitor ALT/AST twice a weekly until Grade \leq 1; restart Tenalisib at one dose lower. and taper steroid. If no immediate response to steroids within 7 days, initiate mycophenolate mofetil. In case of recurrence of transaminitis at reduced doses, discontinue Tenalisib permanently after assessing risk versus benefit. 
Grade \geq 4 Transaminitis (ALT/AST >20 X ULN):
 
 Tenalisib should be permanently discontinued. 
Bilirubin:
 
 Grade \geq 2 ($> 1.5-3$ X ULN): Maintain Tenalisib dose. Monitor at least weekly until \leq 1X ULN Grade \geq 3 ($> 3-10$ X ULN): Withhold Tenalisib. Monitor at least weekly until bilirubin is \leq 1X ULN; restart Tenalisib at one dose lower. Grade \geq 4 (> 10 X ULN): Discontinue Tenalisib permanently
Infection	
Grade 3 or higher sepsis or pneumonia
 
 Interrupt Tenalisib until infection has resolved.
Diarrhea	
Moderate:
 
 Maintain Tenalisib dose. Monitor at least weekly until resolved. 
Severe diarrhoea or hospitalization
 
 Withhold Tenalisib dose. Monitor at least weekly until resolved. Restart Tenalisib at one dose lower. 
Life threatening diarrhoea
 
 Discontinue Tenalisib permanently.
Cardiac	
If a QTcF >500 msec has been demonstrated, hold dose.
 
The patient will be monitored hourly with ECGs until the QTcF <500 msec and the QTcF has returned to "<30 msec from baseline". Immediate attention to potassium and magnesium and other clinical factors such as oxygenation and ischemia should be addressed.
 
All cardiac events should be treated as per the local standard of care and referral to a specialist if clinically indicated. Any final decisions concerning dose modifications or permanently discontinuing the patient from study drug due to QTcF prolongation will occur after discussion with medical monitor.

OTHER NON-HEMATOLOGIC	Action to be Taken
Grade 3/4 CTCAE	
First occurrence: Hold* dose until toxicity Grade \leq 2; restart Tenalisib at one dose lower.
 
Subsequent Occurrences: Hold dose until to \leq Grade 2 or baseline. Discontinue if further dose modification required.

* If study drug is delayed >2 weeks because of an adverse event, treatment strategy should be discussed with medical monitor.

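### Protocol Table 7 does not say whether Tenalisib is held or continued at Grade 3 neutropenia or Grade 3 thrombocytopenia

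*Protocol*

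**What the plan says.** Table 7 (Protocol section 7.7.2.1) governs Tenalisib when the investigator relates a haematologic event to it. Its Grade 3 neutropenia and Grade 3 thrombocytopenia rows carry identical text: "Maintain dose level. Monitor ANC at least weekly. Restart Tenalisib when the event resolved to" Grade 2 or less, or baseline. The Grade 4 neutropenia row differs: "First incidence: Hold* dose until resolved to" that same level, then restart one dose lower. The Grade 4 thrombocytopenia and febrile neutropenia rows also state a hold before the restart. Table 8, in the same section, uses *maintain* for continued dosing in mild transaminitis, "Maintain Tenalisib dose and initiate prednisone 40 mg daily", and keeps *withhold* as a separate step.

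The Grade 3 limits are printed as "1.0 \times 10^9 / L < ANC \geq 0.5 \times 10^9 / L" and "50.0 \times 10^9 / L < PLT \geq 25.0 \times 10^9 / L". The Grade 4 platelet limit is "25.0 \times 10^9 / L < PLT", and the Grade 4 neutrophil limit has the same form with 0.5.

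Section 7.7.1 is headed as criteria for re-starting, but its text says when patients may continue Tenalisib: ANC back at baseline or above 750/µL, and platelets above 50,000/µL.

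Drug interruptions are a planned output. SAP section 10.1 counts patients with interruptions, and SAP section 10.6.2 summarises and lists the adverse events that lead to them.

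**The concern.** A drug that has been maintained cannot be restarted, and one that is to be restarted must first have been stopped. The Grade 3 cells give both ends of that sequence and omit the step that would decide between them. Two sites can therefore treat the same laboratory result in opposite ways, and neither would have deviated from the protocol.

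Two things are at stake. One is patient safety, because the table is the operating rule for a cytopenia during combination treatment. The other is the meaning of the interruption data: if handling differs by site, the counts reflect how the cell was read as well as how toxic the combination is.

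The printed limits and the monitored count raise a smaller concern of the same kind: the cells do not agree with their own row labels.

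**Working it through.** There is no sample size, power or error-rate figure to reproduce. The check sets the texts side by side and evaluates the printed limits literally.

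**1. The action cells**

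| Place | Hold stated? | Restart stated? |
|---|---|---|
| Table 7, Grade 3 neutropenia | No; maintain dose level | Yes, no dose change |
| Table 7, Grade 3 thrombocytopenia | No; maintain dose level | Yes, no dose change |
| Table 7, Grade 4 rows, first occurrence | Yes | Yes, one dose lower |
| Table 7, febrile neutropenia | Yes | Yes, one dose lower |
| Table 8, mild transaminitis | No; maintain, with withholding as a separate later step | No |

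Only the two Grade 3 rows combine maintaining with restarting.

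**2. Does section 7.7.1 settle it?** Unit conversion: 750/µL = 0.75 × 10⁹/L and 50,000/µL = 50 × 10⁹/L.

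- Neutropenia: the apparent Grade 3 band is 0.5 to below 1.0 × 10⁹/L, and 0.75 lies inside it. Read as a rule for continuing, 7.7.1 permits dosing in the upper half of the band and, unless baseline is met, not in the lower half. Read as a rule for restarting, it permits a restart while the patient is still Grade 3, whereas Table 7 asks for Grade 2 or less, or baseline. Neither reading resolves the cell.
- Thrombocytopenia: the apparent band is 25 to below 50 × 10⁹/L, so a criterion above 50 lies outside it. Section 7.7.1 therefore does not fit continued dosing through Grade 3, while the cell still says to maintain. The two places need reconciling.

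**3. The printed limits, read literally (× 10⁹/L)**

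Grade 3 neutropenia requires 1.0 < ANC and ANC ≥ 0.5, which reduces to ANC > 1.0. Grade 4 is ANC > 0.5. Grade 3 thrombocytopenia reduces to PLT > 50, and Grade 4 is PLT > 25. The last two columns reverse the strict sign, only to see whether the rows then match their labels.

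| Count | Grade 3 as printed | Grade 4 as printed | Grade 3, sign reversed | Grade 4, sign reversed |
|---|---|---|---|---|
| ANC 0.3 | no | no | no | yes |
| ANC 0.75 | no | yes | yes | no |
| ANC 4.0 | yes | yes | no | no |
| PLT 10 | no | no | no | yes |
| PLT 30 | no | yes | yes | no |
| PLT 200 | yes | yes | no | no |

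As printed, the lowest counts meet no row and high counts meet both. Inclusion criterion 9 requires ANC ≥ 1,000/µL (1.0) and platelets ≥ 75,000/µL (75). Since 1.0 > 0.5 and 75 > 25, every eligible patient meets both printed Grade 4 expressions at entry. The errors are confined to the strict sign in four cells; the two ≥ lower bounds and the febrile neutropenia limit agree with their labels.

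**4. The monitored count.** The Grade 3 thrombocytopenia row asks for weekly ANC and names no platelet count. Tables 5 and 6 schedule complete blood counts, with platelets under footnote 7, on Days 1, 8, 15 and 22 of Cycles 1 and 2, and on Days 1, 8 and 15 from Cycle 3. The scheduled gap is Day 22 from Cycle 3 onward.

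**5. Size.** The documents do not give the expected number of Tenalisib-related Grade 3 cytopenias on the combination. One patient handled the other way moves the interruption percentage by 1/3 = 33.3 points in a cohort of 3, 1/6 = 16.7 in a cohort of 6, 1/12 = 8.3 in an expansion group and 1/24 = 4.2 across the expansion.

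**The case against.** The best defence is that the cell speaks of the dose *level*. Next to the Grade 4 rows, which restart one dose lower, it can be read as interrupting and then resuming at the same level. That is coherent, but the interruption is not written, and Table 8 uses the verb for continued dosing. The defence shows one possible meaning, not the only one.

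The reach is also narrow. Table 7 applies to events related to Tenalisib; section 7.7.2 asks for the most conservative approach where both drugs may be responsible; and section 7.7.3.1 has its own Romidepsin rule. In the earlier single-agent study (Protocol section 1.1.2), 58 treated patients gave one related neutropenia of Grade 3 or above (1/58 = 1.7%), with no thrombocytopenia listed. The outputs affected are descriptive. All of this stands and limits the size of the point.

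Four stronger readings are tempting, and the documents do not support them:

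- *Dose reductions are also distorted.* Neither reading of the Grade 3 rows lowers the dose, so the ambiguity concerns interruptions only.
- *The reversed limits will lead sites to treat normal counts as Grade 4.* Rows are labelled by grade, and section 7.7 grades all modifications by CTCAE v5.0, so the grade is the working trigger. A PDF reading error is unlikely, since four cells share the pattern and the febrile cell does not, but it cannot be excluded. It would not explain the wording of the action cells.
- *Platelets go unmonitored.* The scheduled blood counts include them.
- *Section 7.7 corroborates the conflict, or resolves it.* Its sentence "Patients may resume Tenalisib, provided that the toxicity has resolved to Grade" 2 or less, or baseline, concerns DLTs and events meeting DLT criteria. Under section 7.6.1, uncomplicated Grade 3 neutropenia or thrombocytopenia is not a haematologic DLT, so the sentence does not reach these rows.

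**Conclusion.** The point holds. Table 7 contains an operating rule that sites can follow in opposite ways: whether Tenalisib is held at Grade 3 neutropenia or Grade 3 thrombocytopenia. No other section fully settles it, least of all for neutropenia. It should be corrected because it touches patient safety and the interpretation of the interruption counts. Sample size, error rates and inferential results are unaffected.

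The reversed strict limits and the ANC-only monitoring instruction are real but secondary drafting errors with limited practical effect.

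The conclusion rests on two assumptions: that the table text was read correctly from the PDF, and that no separate site guidance, absent from these documents, already resolves the cell. No view is taken on which clinical action is right.

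**What to change.** Reconcile the two Grade 3 rows of Table 7 with each other, with the way hold and maintain are used elsewhere in Tables 7 and 8, and with the ANC and platelet criteria in section 7.7.1. Each row should then carry one unambiguous action, chosen by the clinical team. In the same edit, make the four printed limits and the monitored count in the thrombocytopenia row agree with their row labels.

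The cost is a table correction in a protocol amendment, with notice to sites. The SAP needs no change. If patients have already been treated under the present text, the study report should say how Grade 3 cytopenias were handled, so that the interruption counts can be read properly.

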4 SELECTION AND WITHDRAWAL OF SUBJECTS

4.1 Inclusion Criteria

1. Age ≥ 18 years on the day of signing informed consent.
2. Pathologically confirmed T-cell lymphoma at the enrolling institution*.
3. Disease status as defined as relapsed after or refractory to at least one systemic therapy.

4. The patients should have received NOT more than three prior systemic combination chemotherapies.
5. Must have ECOG performance status ≤ 2 .
6. PTCL patients must have measurable disease as defined at least one bi-dimensional measurable lesion with minimum measurement of > 1.5 cm in the longest diameter.
7. Life expectancy of at least 3 months.
8. Toxicities related to prior therapy must have returned to **Grade 1 or less**, except for alopecia.
9. Adequate bone marrow, liver and renal function in line with below mentioned laboratory requirements. Hemoglobin and platelet requirements should not be met by use of recent transfusion or growth factor support (GCSF or erythropoietin) within 3 weeks prior to treatment initiation.
 - Hemoglobin ≥ 8.0 g/dL
 - Absolute neutrophil count (ANC) $\geq 1,000/\mu\text{L}$
 - Platelet count $\geq 75,000/\mu\text{L}$
 - Total bilirubin ≤ 1.5 times the ULN (or $\leq 3 \times$ ULN, if patient has Gilbert syndrome)
 - AST (SGOT) and ALT (SGPT) $\leq 3 \times$ ULN; ≤ 5 ULN in case of liver involvement
 - Calculated creatinine clearance (CrCl) > 50 ml/min by Cockcroft-Gault formula.
10. Use of an effective means of contraception for women of childbearing potential and men with partners of childbearing potential.
11. Female subject of childbearing potential should have a negative urine or serum pregnancy within 72 hours prior to receiving the first dose of study medication. If the urine test is positive or cannot be confirmed as negative, a serum pregnancy test will be required.
12. Provide written informed consent prior to any study-specific screening procedures.
13. Willingness and capability to comply with the requirements of the study.

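### Table 8's hepatic rows give no clear rule for ALT/AST >3-5 x ULN, and their restart limits conflict with Section 7.7.1 and with baselines that eligibility allows

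*Protocol*

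**What the plan says.** **Table 8, hepatic row (printed under 7.7.2.1).** The transaminitis entries are headed Grade ≥1 (>1-3 x ULN), Grade ≥3 (>5-20 x ULN) and Grade ≥4 (>20 x ULN). The first says "Maintain Tenalisib dose and initiate prednisone 40 mg daily", with weekly monitoring, and ends with "Withhold Tenalisib in case of development of grade 2 transaminitis or worsening of Grade 1 transaminitis while on steroids". The second says "Withhold Tenalisib and monitor ALT/AST twice a weekly until Grade" 1 or lower, then restart one dose level down. The third stops Tenalisib for good. The bilirubin entries are headed Grade ≥2 (>1.5-3 x ULN, maintain), Grade ≥3 (>3-10 x ULN, withhold until at or below 1 x ULN, then one level down) and Grade ≥4 (>10 x ULN, stop permanently). An asterisk on the row calls for discussion with the medical monitor after a delay of more than 2 weeks.

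**Section 7.7**, after a sentence about DLTs and later events that meet DLT criteria: "Patients may resume Tenalisib, provided that the toxicity has resolved to Grade" 2 or lower, or baseline.

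**Section 7.7.1**, among the conditions for continuing Tenalisib: "Recovered from grade 3-4 non-hematologic toxicity to grade 2 or baseline (excluding alopecia".

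**Section 4.1, criterion 9.** Bilirubin may be up to 1.5 x ULN, or 3 x ULN "if patient has Gilbert syndrome". ALT/AST may be up to 3 x ULN, or 5 x ULN "in case of liver involvement".

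**Section 7.6.2.** Grade ≥3 ALT/AST that settles to Grade 2 or lower within 14 days is not a DLT. A treatment delay of 14 days or more for toxicity that has not resolved is one.

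**The concern.** Liver enzyme elevation was the most frequent treatment-related Grade ≥3 event reported for Tenalisib in Section 1.1.2 (n=12, against n=4 for rash), so these rows will be used. If two sections give different answers for one laboratory value, sites can treat the same event differently while each follows the protocol.

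That is first a patient-safety matter. It also affects the data. SAP Sections 10.1, 10.6.1 and 10.6.2 summarise exposure, interruptions, reductions and permanent withdrawals by cohort and group, and those counts would partly reflect which passage a site followed. In Cycle 1 of dose escalation, the length of a hold can itself count as a DLT, and in a 3+3 design one DLT can change a cohort decision.

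**Working it through.** No sample-size or power figure is involved. The check runs liver values through each passage. Grades are taken from Table 8's own bands. For ALT/AST, Grade 1 is >1-3, Grade 2 is the range left between bands (>3-5), Grade 3 is >5-20 and Grade 4 is >20 x ULN. For bilirubin, Grade 2 is >1.5-3, Grade 3 is >3-10 and Grade 4 is >10 x ULN, with >1-1.5 x ULN below these taken as Grade 1.

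**1. Which row applies?**

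| ALT/AST (x ULN) | Printed bands containing it | Grade headings it satisfies |
|---|---|---|
| 2.9 | >1-3 | ≥1 |
| 4 | none | ≥1 |
| 10 | >5-20 | ≥1, ≥3 |
| 25 | >20 | ≥1, ≥3, ≥4 |

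The bands never overlap; only the ≥ signs do. Bilirubin shows the same pattern: >3-10 satisfies two headings and >10 satisfies three, but each lies in one band. Reading by band settles every value in the transaminitis rows except >3-5 x ULN.

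Take a first presentation at 4 x ULN in a patient not on steroids. By band there is no row. By heading the first instruction is to maintain. The bullet means withhold if the steroid phrase limits only the worsening of Grade 1, and it does not apply if the phrase limits both halves. If the dose is withheld, the row gives no restart limit and no restart dose. Section 7.7.1's recovery condition concerns Grade 3-4 events, so it does not supply one for a Grade 2 hold.

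**2. When may Tenalisib restart after a Grade 3 liver event?**

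| Value during recovery (x ULN) | Table 8 | 7.7.1 recovery condition |
|---|---|---|
| ALT/AST 2.9 | met (Grade 1) | met |
| ALT/AST 4 | not met (Grade 2) | met |
| Bilirubin 1.0 | met | met |
| Bilirubin 1.2 | not met (above 1) | met |
| Bilirubin 2 | not met | met (Grade 2) |

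The two rules disagree over ALT/AST >3-5 x ULN and bilirubin >1-3 x ULN. For Grade 4, Table 8 stops permanently, while 7.7.1 includes Grade 4 events that have recovered. For events meeting DLT criteria, 7.7 sets the same Grade 2 or baseline limit as 7.7.1.

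**3. Can the difference reach a DLT?** Suppose ALT/AST falls from Grade 3 to Grade 2 within 14 days. The elevation itself is exempt under 7.6.2. Under 7.7.1 dosing may resume. Under Table 8 the hold goes on to Grade 1 and can reach 14 days, which is a separate DLT criterion. For a full 14-day hold to fall inside the 28-day window it must start by about Day 15 (Days 15 to 28 are 14 days), unless the window is extended. So this applies to early Cycle 1 events only.

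**4. What happens to a patient who returns exactly to an abnormal eligible baseline?**

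| Group | Eligible up to | Table 8 restart limit | Baselines that fail it |
|---|---|---|---|
| Bilirubin, no Gilbert syndrome | 1.5 x ULN | 1 x ULN | >1-1.5 |
| Bilirubin, Gilbert syndrome | 3 x ULN | 1 x ULN | >1-3 |
| ALT/AST, liver involvement | 5 x ULN | Grade 1 (3 x ULN by the bands) | >3-5 |

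All three groups satisfy 7.7.1 at baseline. The bilirubin rows of this table need no grading assumption, because the limit is printed as a multiple of ULN. The ALT/AST row does.

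**5. Frequency.** 12/58 = 20.7%. At the planned maximum of 18 + 24 = 42 patients, 0.207 x 42 = 8.7, or about 9 patients with Grade ≥3 ALT/AST if the rate carried over. The source is a single-agent study at 200 to 800 mg BID, so this is an illustration.

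**The case against.** **The headings are only a labelling slip.** This stands. A reader might infer that 25 x ULN could be handled three ways, from maintaining the dose to stopping it. The printed bands do not support that: 25 x ULN lies only in the >20 row. The ≥ signs should be corrected, but the unresolved range is >3-5 x ULN.

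**The specific rule overrides the general one.** Table 8 has a separate row for other non-hematologic Grade 3/4 events with a Grade 2 limit, which suggests that the hepatic limits were meant to be stricter. Section 7.7.1 is also permissive and leaves continuation to the investigator. This is a reasonable reading, but no section states it. The instruction in 7.7.2 to take the most conservative approach covers only events possibly related to both drugs.

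**Section 7.7 is narrower than it looks.** This stands. Its resumption sentence follows one about DLTs and events meeting DLT criteria, and Grade ≥3 ALT/AST that settles within 14 days is exempt from those. The general conflict is therefore with 7.7.1.

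**Patients held at baseline are covered.** A reader might infer that they lose Tenalisib permanently after full recovery. The text does not say so. Table 8 keeps them withheld, with medical-monitor discussion after more than 2 weeks. Permanent stopping is kept for the highest bands and, for transaminitis, recurrence at a reduced dose after a risk-benefit assessment. The safeguard limits the harm, but it starts late and gives no rule for the first two weeks.

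**Grades may depend on baseline.** CTCAE v5.0 governs grading and is not reproduced in the protocol. If it grades relative to an abnormal baseline, the ALT/AST part of step 4 could fall away. The bilirubin part would not.

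**Conclusion.** The point holds in three parts. First, ALT/AST >3-5 x ULN has no band, an ambiguous instruction and no restart rule. Second, after Grade 3, Table 8 and 7.7.1 disagree for ALT/AST >3-5 x ULN and bilirubin >1-3 x ULN, and they disagree on whether Grade 4 can ever be followed by a restart; precedence is not stated. Third, eligible patients with baseline bilirubin >1-1.5 x ULN, or >1-3 x ULN with Gilbert syndrome, do not meet Table 8's limit on returning to baseline. The same is true of ALT/AST >3-5 x ULN with liver involvement, on the assumption that grades follow Table 8's bands whatever the baseline.

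A reader might take the 21% as the size of the whole problem. It counts Grade ≥3 events, so it bears only on the restart conflict. The documents give no frequency for Grade 2 events or for abnormal eligible baselines. An effect on a cohort decision is possible rather than expected: it needs an early Cycle 1 event, and the Safety Review Committee may decide, with documented reasons, not to count a DLT.

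This should be corrected, because it concerns patient safety and is cheap to repair. No view is taken on which limit or action is clinically right.

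**What to change.** Amend the protocol so that the passages agree:

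- Make each ALT/AST and bilirubin heading a single grade that matches the x ULN band beside it.
- State one action and one restart rule for ALT/AST >3-5 x ULN, and make clear whether prior steroid use changes them.
- Reconcile Table 8's hepatic restart limits and its Grade 4 rule with 7.7 and 7.7.1, or state which passage governs liver events. Say also how a hold under that rule counts toward the 14-day delay criterion in 7.6.2.
- State how the restart limit applies to patients admitted above it under criterion 9.

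The thresholds and actions are for the sponsor to set. The cost is rewording one table block and adding cross-references in 7.6.2, 7.7 and 7.7.1 by amendment, with no new assessments.
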